5.2.1 Disease Related Criteria

1. Histologically or cytologically confirmed adenocarcinoma of the prostate without neuroendocrine differentiation or small cell features.
2. Patients with systemic PCa as defined by either a) hormonal naïve metastatic PCa with radiographic evidence of visceral or osseous metastasis or b) biochemical recurrence PCa that fulfills **all** of the following criteria:
 - A minimum of three rising PSA levels with an interval of \geq 1 week between each test.
 - The PSA value at the screening visit should be \geq 2 ng/ml.
 - PSA doubling time \leq 9 months.
3. Patients should be 65 years or older.
4. Patients who are deemed “not fit” by CGA or at high risk for side effects from ADT as determined by the treating physician. **A case report form will be used to document the specifics of why each eligible patient is not considered an ideal candidate for ADT.**
5. Serum testosterone level > 1.7 nmol/L (50 ng/dL) at the screening visit (non-castrate)

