10.3.2 Changes in Comprehensive Geriatric Assessment

Analysis of this aim will be descriptive and will describe mean, median, standard deviations of scores at baseline and at follow up time points. CGA deficits over 6 months will be captured. Each domain will be evaluated individually and scores will be compared between baseline and 6 months. Overall CGA deficits will be examined and the proportion of patients who decline in more than 1 domain will be determined for these time points.

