16.6 Appendix E: Comprehensive Geriatric assessment tools

 Participant ID	Geriatric Assessment for Older Cancer Patients			 Participant Initials
Orientation-Memory-Concentration Test				
Directions: Please answer the following questions. DO NOT use a pencil, black pen is preferred. Choose only one answer to each question.				
	Maximum Errors	Score x Weight	Final Score	
1. What year is it now:		1	 x 4 =	
2. What month is it now:		1	 x 3 =	
Repeat this phrase after me:				
John Brown, 42 Market Street, Chicago				
3. About what time is it (within one hour):	 : 	1	 x 3 =	
4. Count backwards 20 to 1:		2	 x 2 =	
5. Say the months in reverse order:		2	 x 2 =	
6. Repeat the phrase just given:		5	 x 2 =	
Total error score =  /28				

Scoring

Items 1 - 3: response correct = 0, incorrect = 1

[figure not shown]
Items 4 - 6: subtract 1 point for each error (for 4 and 5 max error is 2, for 6 max error is 5)

Total all scores. Greater or equal to 11 equals cognitive impairment

Participant ID

Geriatric Assessment for Older Cancer Patients
Vulnerable Elder's Survey -13

Participant Initials

Directions: Please answer the following questions. DO NOT use a pencil, black pen is preferred.
Choose only one answer to each question.

1a. Age

1b. In general, compared to other people your age, would you say that your health is:
 Poor Fair Good Very good Excellent

2. How much difficulty, on average, do you have with the following activities:

	No difficulty	A little difficulty	Some difficulty	A lot of difficulty	Unable to do
a. stooping, crouching, or kneeling					
b. lifting, or carrying objects as heavy as 10 pounds					
c. reaching or extending arms above shoulder level					
d. writing, handling, or grasping small objects					
e. walking a quarter of a mile					
f. heavy housework such as scrubbing floors or washing windows					

Because of your health or physical condition, do you have any difficulty:

3. shopping for personal items (like toilet items or medicines)?

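### The cognitive test form tells the assessor to subtract points for errors on items 4 to 6, against the direction of its own error score and cut-off

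*Combined protocol and SAP*

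**What the plan says.** The form is in Appendix E (Section 16.6) of the combined protocol and SAP. It has six items. Each has a ceiling in a column headed "Maximum Errors", a score box multiplied by a weight, and a final score. The bottom line is a "Total error score" out of 28.

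Three scoring notes follow:

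- For the first three items: "Items 1 - 3: response correct = 0, incorrect = 1".
- For the last three: "Items 4 - 6: subtract 1 point for each error (for 4 and 5 max error is 2, for 6 max error is 5".
- For the total: "Total all scores. Greater or equal to 11 equals cognitive impairment".

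The domain table in Section 9.3.2 lists this test as the BOMC, with impairment at a score above 10. For whole-number scores that is the same cut-off as 11 or more. The same table gives the MoCA, with impairment below 26, as the second cognition tool.

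Section 10.3.2 describes the analysis: means, medians and standard deviations at baseline and follow-up, the proportion of patients who decline in more than one domain, and this comparison: "Each domain will be evaluated individually and scores will be compared between baseline and 6 months". Section 2.3 places this objective among the tertiary, exploratory ones.

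**The concern.** Two adjacent scoring notes run in opposite directions. On items 1 to 3 a wrong answer adds to the score. On items 4 to 6 an error takes away from it. Yet the six item scores are summed and read against a single cut-off where higher is worse.

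Cognitive change is one of the harms of androgen deprivation that Section 9.3.2 wants the geriatric assessment to track. An assessor who follows the note as printed would record a real loss of attention or recall on items 4 to 6 as a fall in the total, that is, as an improvement. The change scores in Section 10.3.2, the descriptive statistics and the count of patients declining in more than one domain would all carry that reversal. Section 6.0 has a geriatric oncologist or a designee administer the assessment at each of two sites, so the printed scoring line is what keeps scorers consistent. No other section corrects it.

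**Working it through.** **Inputs, all from the Appendix E form**

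| Item | Maximum errors | Weight | Maximum weighted score |
|---|---|---|---|
| 1 Year | 1 | 4 | 4 |
| 2 Month | 1 | 3 | 3 |
| 3 Time | 1 | 3 | 3 |
| 4 Count backwards | 2 | 2 | 4 |
| 5 Months reversed | 2 | 2 | 4 |
| 6 Repeat phrase | 5 | 2 | 10 |

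**Step 1. Reproduce the form's maximum.** 4 + 3 + 3 + 4 + 4 + 10 = 28, as printed. Items 4 to 6 contribute 4 + 4 + 10 = 18, and 18/28 = 64% of the score.

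**Step 2. Write out the possible rules.** Let e1 to e6 be the errors on each item, A = 4e1 + 3e2 + 3e3, and E = e4 + e5 + e6. The form gives no starting value to subtract from, so both natural choices are shown.

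- Errors added: T = A + 2E
- Subtracted from zero: T = A − 2E
- Subtracted from the item maximum: T = A + 2[(2 − e4) + (2 − e5) + (5 − e6)] = A + 18 − 2E

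**Step 3. Put in four reference patterns** and classify at 11 or more.

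| Pattern | Added | From zero | From maximum |
|---|---|---|---|
| No errors (A = 0, E = 0) | 0, not impaired | 0, not impaired | 18, impaired |
| Items 1–3 wrong only (A = 10, E = 0) | 10, not impaired | 10, not impaired | 28, impaired |
| Items 4–6 wrong only (A = 0, E = 9) | 18, impaired | −18, not impaired | 0, not impaired |
| Everything wrong (A = 10, E = 9) | 28, impaired | −8, not impaired | 10, not impaired |
| Range over all patterns | 0 to 28 | −18 to 10 | 0 to 28 |

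Subtracting from zero, the ceiling is 10, so the cut-off of 11 cannot be reached. Subtracting from the maximum, all four reference classifications are reversed.

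**Step 4. Effect on change.** Each further error on items 4 to 6 moves the total by +2 when errors are added and by −2 under either literal reading. Three more errors on item 6 between baseline and 6 months would be +6 (worse) or −6 (apparently better).

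**Step 5. What identifies the error.** The figure of 28 does not settle it alone: subtracting from the maximum also yields totals from 0 to 28, but 28 then means items 1 to 3 wrong and items 4 to 6 perfect. The contradiction is one of direction. Only adding errors makes the total an error score in which higher is worse throughout, as the total line and the cut-off require.

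**The case against.** The strongest reply is that the form explains itself. The column of error ceilings, the total labelled as an error score out of 28, the cut-off, and the matching threshold in Section 9.3.2 all point to adding. The disputed note itself caps errors at 2, 2 and 5. With no starting value printed, it cannot be carried out as written, and both literal readings have to supply one. A trained assessor would probably add. This stands, and it limits the point to a wording error with a conditional consequence.

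Three stronger readings are tempting, and the documents do not support them.

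- A reader might infer that cognition has been misclassified in this trial. Nothing in the documents shows how any form was scored.
- A reader might enumerate the 2 × 2 × 2 × 3 × 3 × 6 = 432 error patterns, find that subtracting from the maximum misclassifies 182 of them, and take that as an error rate. It is not one. Every pattern gets equal weight, and 323 of the 432 count as impaired even when errors are added. Only the direction of the conflict is informative.
- A reader might infer that patients could be wrongly enrolled, because criterion 4 in Section 5.2.1 admits those who are not fit "by CGA or at high risk for side effects from ADT as determined by the treating physician". No section sets a BOMC threshold for being not fit, physician judgement is an alternative route, and Section 5.1 describes the decision as the treating physician's.

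It is also true that the endpoint is tertiary and descriptive and that the MoCA covers cognition independently. That reduces the stakes, but it does not correct the BOMC summaries that Section 10.3.2 would report.

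**Conclusion.** Wrong as written, and minor. The note for items 4 to 6 contradicts the error-score structure of its own form on 18 of 28 points. Followed literally, it makes decline on those items look like improvement, and it either puts the cut-off out of reach or classes a flawless patient as impaired (18) and a patient with everything wrong as unimpaired (10).

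These consequences hold only if an assessor follows the note rather than the rest of the form, and they depend on which starting value is assumed. Adding is the evident intent. The effect is confined to the descriptive geriatric assessment analysis in Section 10.3.2, with no shown effect on eligibility, the primary endpoint, the sample size or power.

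**What to change.** Reword the note so that items 4 to 6 score (add) 1 point for each error, to a maximum of 2, 2 and 5, and state that the total runs from 0 to 28 with higher worse. Notify both sites.

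Before the Section 10.3.2 analysis, verify at item level how completed forms were scored, and correct item scores where the direction was reversed and the entries allow it. Totals alone are not enough: negative totals reveal subtraction from zero, but subtraction from the maximum gives plausible totals between 0 and 28. Where the scorer's rule is known, the conversion is simple: errors are the absolute value of a score taken from zero, or the item maximum minus a score taken from the maximum.

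The wording change is one word plus a line on the form, and a note to the sites. The cost of the check is less certain. Items 4 to 6 have a score box and a final-score box but no separate field for raw errors, so some forms may not be recoverable if neither the item entries nor the scoring rule can be established. Any such forms should be counted and reported with the analysis.

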9.3.2 Change in CGA Domains

ADT, which includes orchiectomy or administration of GnRH agonists/antagonists, remains the mainstay of treatment for hormone naïve patients who present with biochemical recurrence or metastatic disease. Testosterone depletion secondary to ADT causes a myriad of side effects, which include decreased libido, muscle strength, increased risk of falls and cognitive changes. All these changes have been well characterized and captured using a CGA in numerous studies. The current trial would be utilizing periodic CGA to capture any side effects related to the study drug combination that would otherwise not be recognized to provide a better understanding of the safety profile of the drug combination specifically in the vulnerable/frail elderly population.

During geriatric assessments, the various domains as listed in the table below will be measured

DOMAIN	TOOL	SCORE SIGNIFYING IMPAIRMENT
Physical function	➤ ADL ➤ IADL ➤ Fall history	➤ Any ADL or IADL impairment ➤ Any history of fall

Objective physical performance	➤ SPPB	➤ ≤ 9
Comorbidity	➤ Average number of comorbid conditions	➤ > 5
Nutrition	➤ BMI ➤ MNA	➤ <21 ➤ ≤ 11
Social support	➤ OARS Medical Social Support	➤ Any deficit noted
Polypharmacy	➤ Number of total medications	➤ ≥ 5 medications
Psychological	➤ GDS	➤ ≥ 5
Cognition	➤ BOMC ➤ MoCA	➤ > 10 ➤ <26
Screening	➤ VES-13	➤ ≥ 3

ADL: Activity of daily living

MNA: Mini nutritional assessment

SPPB: Short physical performance battery

BMI: Body mass index

VES: Vulnerable elderly survey

GDS: Geriatric Depression scale

IADL: Instrumental activity of daily living

BOMC: Blessed orientation-memory-concentration

MoCA: Montreal cognitive assessment

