14.6 Selection of Timing of Dose for Each Patient

Enzalutamide is administered orally once daily. Enzalutamide should be taken as close to the same time each day as possible and can be taken with or without food. The capsules should be swallowed whole and not chewed or opened

Dutasteride or Finasteride is to be co-administered with enzalutamide and taken once daily as well. The capsules should be swallowed whole and not chewed or opened, as contact with the capsule contents may result in irritation of the oropharyngeal mucosa. Dutasteride can be administered with or without food. **If dosing of either drug is missed on one day for any reason, double-dosing should NOT occur the following day.** Patients should hold their dose of study drug as instructed by the treating physician.

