2. I do activities to improve flexibility, such as stretching or yoga, once a week or more. Yes No

RAPA 1

RAPA 2

1879324352

1 / 1

[name] 04/19/2011

--	--	--

Participant I.D.

Geriatric Assessment for
Older Cancer Patients

--	--	--

Participant Initials

Falls

Place an 'X' in one (1) answer to each question.

1. In the past year, have you fallen down?

Yes Refused
 No Don't Know

If you answered yes to question one, please complete the rest of this page.

2. About how long ago was your most recent fall?

--	--

 months ago

3. In the past year, how many times have you fallen down?

--	--	--

Refused
 Don't Know

4. In that fall or any of those falls, did you hurt yourself badly enough to get medical help?

Yes Refused
 No Don't Know

5. Did you talk to a doctor or other medical professional about that fall or any of those falls?

Yes Refused
 No Don't Know

6. Did the health care provider talk with you to understand why you fell?

Yes Refused
 No Don't Know

[figure not shown]
7. Did the health care provider talk with you about how to prevent future falls?

Yes Refused
 No Don't Know

9965611973

[figure not shown]
Page 1 of 1

[name] 11/28/2012

Participant I.D.

Geriatric Assessment for Older
Cancer Patients
Geriatric Depression Scale

Participant Initials

Instructions: Please check one response for each question.

1. Are you basically satisfied with your life? Yes No
2. Have you dropped many of your activities and interests? Yes No
3. Do you feel that your life is empty? Yes No
4. Do you often get bored? Yes No
5. Are you in good spirits most of the time? Yes No
6. Are you afraid that something bad is going to happen to you? Yes No
7. Do you feel happy most of the time? Yes No
8. Do you often feel helpless? Yes No
9. Do you prefer to stay home, rather than going out and doing new things? Yes No
10. Do you feel you have more problems with memory than most? Yes No
11. Do you think it is wonderful to be alive now? Yes No
12. Do you feel pretty worthless the way you are now? Yes No
13. Do you feel that your life is full of energy? Yes No
14. Do you feel that your situation is hopeless? Yes No
15. Do you think that most people are better off than you are? Yes No

--	--	--

Participant ID

Geriatric Assessment for
Older Cancer Patients

--	--	--

Participant Initials

Sarcopenia

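### Early follow-up falls scores reach back before treatment and so dilute change, and the medication count does not exclude the two study drugs

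*Combined protocol and SAP*

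**What the plan says.** The comprehensive geriatric assessment (CGA) is done at baseline, at the end of cycle 1, every 24 weeks until week 61, and at progression (section 8.0, CGA footnote). Section 9.3.2 gives it a safety purpose: to pick up side effects of the combination that would otherwise be missed.

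**Falls.** Fall history is one of three tools in the physical function domain, with ADL and IADL. The entry that signifies impairment is "Any history of fall" (section 9.3.2). The only falls form, in Appendix E, asks "In the past year, have you fallen down". A man who answers yes is also asked "About how long ago was your most recent fall", in months, and "In the past year, how many times have you fallen down". No separate follow-up form or shorter window is given.

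**Polypharmacy.** The tool is "Number of total medications" and impairment is "≥ 5 medications" (section 9.3.2). On treatment, "Dutasteride or Finasteride is to be co-administered with enzalutamide and taken once daily as well" (section 14.6), so protocol treatment is two daily drugs. The medication list form is named in Appendix E as an attachment and is not reproduced, so its counting rule cannot be read.

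**Analysis.** Section 10.3.2 is descriptive. It compares each domain between baseline and 6 months and adds that "the proportion of patients who decline in more than 1 domain will be determined for these time points". It does not define decline, does not use the recency question, and does not say how study drugs are treated in the medication count.

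**The concern.** A before-and-after comparison needs the after measurement to describe the time on treatment. A past-year falls question asked 3 or 6 months into treatment describes a mixture. A man who fell a month before entry still answers yes at 6 months whether or not he has fallen since. If he stopped falling, the improvement is hidden; if he fell again, the yes/no item shows nothing new.

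The medication count has a different problem. If the study drugs are included, the score moves because the man was enrolled, not because his health changed.

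Falls are among the protocol's main reasons for avoiding ADT (sections 1.0 and 9.3.1), and multiple falls were a reason for withholding it in the site's own retrospective series (section 1.2). Men chosen this way may include many recent fallers, in whom the item is least able to show change. At stake is how the CGA findings are read as safety evidence, in either direction.

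**Working it through.** The plan gives no precision or sample-size figure for the CGA, so there is none to reproduce.

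**1. Share of the recall window before treatment.** Share = max(0, 52 − weeks on drug) / 52.

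| Assessment | Weeks on drug | Share before Day 1 |
|---|---|---|
| End of cycle 1 (week 13) | 12 | 40/52 = 77% |
| Nominal 6 months (week 25) | 24 | 28/52 = 54% |
| Week 37 | 36 | 16/52 = 31% |
| Week 61 | 60 | 0% |

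The footnote (end of cycle 1, then every 24 weeks to week 61) fits weeks 13, 37 and 61 best. The 6-month comparison in 10.3.2 therefore has an overlap of 54% if an assessment is made then, or 31% if week 37 stands in for it.

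**2. Direction.** A man with no fall in the year before baseline who later answers yes must have fallen after baseline. Overlap therefore cannot produce a false new impairment. It can only keep a yes in place.

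**3. Size.** The assumptions are a constant fall rate before treatment and a share p reporting a past-year fall at baseline. Section 9.3.2 cites a series of men on ADT in which 22% reported falls, with no recall window stated. I take p = 22% and show 15% to 40%. With a rate multiplier m on treatment, at exactly half a year:

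- past-year item: 1 − (1−p)^(0.5 + 0.5m)
- any fall in the 6 months on treatment: 1 − (1−p)^(0.5m)
- any fall in the 6 months before baseline: 1 − (1−p)^0.5

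| p | Past-year item, m = 2 | Equal 6-month windows, m = 2 | Past-year item, m = 0.5 | Equal 6-month windows, m = 0.5 |
|---|---|---|---|---|
| 15% | 15% → 21.6% | 7.8% → 15.0% | 15% → 11.5% | 7.8% → 4.0% |
| 22% | 22% → 31.1% | 11.7% → 22.0% | 22% → 17.0% | 11.7% → 6.0% |
| 40% | 40% → 53.5% | 22.5% → 40.0% | 40% → 31.8% | 22.5% → 12.0% |

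At p = 22%, a true doubling appears as a ratio of 31.1/22 = 1.41 on the past-year item and 22.0/11.7 = 1.88 over equal windows.

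**4. No falls at all on treatment.** The share still answering yes after 24 weeks is 1 − (1−p)^(28/52). At p = 22% this is 12.5%, or 5 of 40 men. For p from 15% to 40% it is 3.4 to 9.6 of 40.

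**5. Medication count.** If study drugs are counted, 3 + 2 = 5 and 4 + 2 = 6, so a man on 3 or 4 other medicines reaches the cut-off on Day 1. The baseline distribution is not given. If 10% to 40% of men are on 3 or 4, that is 4 to 16 of 40.

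**6. Effect on the summary proportion.** Section 9.3.2 lists nine domains, so polypharmacy leaves eight others. Assume each declines independently with probability d. Without a built-in decline a man needs at least 2 of the 8; with one he needs at least 1.

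| d | At least 2 of 8 | At least 1 of 8 |
|---|---|---|
| 5% | 6% | 34% |
| 10% | 19% | 57% |
| 20% | 50% | 83% |

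The left column is that man's chance of being counted without the polypharmacy shift, and the right column is his chance with it.

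**The case against.** **The obvious repair is worse than the fault.** If follow-up were scored on falls since Day 1 while baseline stayed a 12-month item, no effect at all would read as 22% to 12%, and a true doubling as 22% to 22%. This objection stands, and it is why the windows must be equal.

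**The information is already collected.** The recency question tells whether the latest fall came after Day 1, so the yes/no item can be re-dated to within a month. This also stands: the gap is mainly in the analysis text. The recency question cannot date earlier falls within the past-year count.

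**Falls are only one of three tools in the domain, and decline is undefined.** In the cited series 24% had ADL and 42% had IADL impairment, so many men may be impaired in physical function whatever the falls item says. The dilution above is therefore for the falls item; the effect on the domain will be smaller.

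**A reader might infer that the plan counts the study drugs.** It does not say so, and the form cannot be read. Counting them is the natural reading of a total, the more so because section 14.4 has the 5-AR inhibitor dispensed on prescription from a retail pharmacy. It is still a reading.

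**A reader might also infer that every man on 3 or 4 medicines must cross.** The documents do not support that. Section 5.3.2 allows a short course of a first-generation antiandrogen before the start, which could be on the baseline list and later drop off. Section 12.0 also provides for the 5-AR inhibitor to be held permanently.

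**The stakes are limited.** The endpoint is tertiary, descriptive and single-arm, and untoward events after the first dose are also recorded as adverse events (section 11.0). That lowers the priority but does not remove the reason to fix the scoring.

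**Conclusion.** The point holds in a limited form. On falls, the recall window reaches back before treatment at the early follow-up assessments, and 10.3.2 has no rule to separate the two periods. At 6 months a doubled fall rate would show as 22% to 31% instead of 12% to 22%, assuming 22% at baseline and a constant rate. Over a 15% to 40% baseline the direction and rough size stay the same.

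Two stronger readings of the falls item are not supported. The overlap does not manufacture decline; it hides change. Nor does it affect every assessment, because on the form's past-year window it is gone by week 61.

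The medication point is conditional: the plan does not say that the study drugs are excluded. If they are counted, the shift comes from being assigned treatment, and it acts in the direction of decline. Its size depends on a baseline distribution that the documents do not give.

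Both matter for reading CGA change as safety evidence. Neither touches PSA progression-free survival.

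**What to change.** Add to section 10.3.2:

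1. **Falls.** Compare equal windows, using the recency question at both assessments: for example, any fall in the 6 months before baseline against any fall in the first 6 months on treatment. If week 37 serves as the follow-up point, use the matching number of months on each side. Do not set a since-Day-1 score against a 12-month baseline score.
2. **Fall rate.** Report falls per person-time on treatment beside the baseline past-year rate. Because the past-year count cannot be split before week 61, this needs a follow-up question on the number of falls since Day 1 or since the last assessment.
3. **Medications.** Exclude enzalutamide and the 5-AR inhibitor from the follow-up count, and state how a pre-study antiandrogen on the baseline list is handled. Compute the proportion declining in more than one domain on that basis; showing it both ways is optional.
4. **Decline.** Define it for each domain, including how falls combine with ADL and IADL.

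The cost is a few scoring sentences, one extra question on the follow-up form and slightly more analysis. No visits or patients are added. Men already assessed can be re-scored on the yes/no falls item. The limitation is month-level rounding and recall error in dating the latest fall.
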